3.3 Recruitment Strategy and Patient Screening

All patients presenting to participating surgeons between the ages of 18 to 50 years with a tibial or femoral shaft fracture will be screened. Potentially eligible patients will be approached to participate in the trial. All screened patients will be classified as included or excluded.

3.4 Randomization Methods

Each participant will be randomized to 1 of 4 treatment groups: 1) 150,000 IU loading dose vitamin D₃ plus daily dose placebo; 2) loading dose placebo plus 4,000 IU vitamin D₃ per day; 3) loading dose placebo plus 600 IU vitamin D₃ per day; or 4) loading dose placebo plus daily dose placebo. The daily vitamin D₃ supplements/placebo will be provided in a blinded manner. The daily treatment will commence within 1 week of injury and will be taken for 3 months. The loading dose vitamin D₃ supplements/placebo will be given within 1 week of injury and at 6 weeks (+/- 2 weeks) post-injury.

Allocation to the 4 study groups will be concealed using a centralized 24-hour computerized randomization system that will allow internet-based allocation. The treatment allocation will be stratified on the following prognostic factors to ensure balance between the intervention groups: fracture type (closed vs. open) and long bone fracture (tibia vs. femur).

3.5 Vitamin D₃ (Cholecalciferol) Treatment Groups

3.5.1 Blinded administration

The loading dose of 150,000 IU will consist of 3 50,000 IU capsules of vitamin D₃. The loading dose placebo will consist of 3 capsules that are identical to the 50,000 IU capsules with no active ingredient. The loading dose vitamin D₃ supplements/placebo will be given within 1 week of injury and at 6 weeks (+/- 2weeks) post-injury while in hospital or at the outpatient fracture clinic.

The daily vitamin D₃ supplements/placebo will be provided in a blinded manner and the daily treatment will commence within 1 week of injury. The daily doses (4,000 IU, 600 IU, and placebo) will be identical and will be comprised of one capsule. Patients will be given a bottle of either active vitamin D₃ or placebo capsules and will be instructed to take one capsule daily for 3 months. The placebo capsules will have no active ingredients and will be identical to the vitamin D capsules. To measure supplementation adherence, participants will be asked to bring their bottles to their follow-up visits. At the 3-month visit, participants will return their bottle to the clinical research coordinator. If the participant does not return the bottle, the clinical research coordinator will provide them with an envelope to return it via mail.

All doses of vitamin D and placebo will be obtained from Bio-Tech Pharmacal, Inc. (Fayetteville, AK). The unblinding protocol can be found in **Figure 3**. Following the completion of the study, participants may be unblinded their treatment group upon request.

3.5.2 Vitamin D₃ dose rationale

The doses selected are based on biologic rationale, current practice patterns, and existing guidelines. The goal of the high dose arms is to rapidly increase circulating vitamin D and serum 25(OH)D during the early callus fracture healing periods. Conversely, while the low daily dose is not expected to increase circulating vitamin D as quickly as the high dose strategies, this treatment arm will determine if rapid serum increases are necessary to improve fracture healing. Finally, the placebo control arm is needed to demonstrate the

relative efficacy of each treatment arm and is also necessary to represent current practice at most trauma centers in North America.

- High loading dose: 150,000 IU D₃ loading doses can be administered easily with three 50,000 IU D₃ pills. We expect this dose to increase circulating vitamin D levels the fastest. While we acknowledge that many non-orthopaedic clinicians may prefer more frequent large doses, such as 50,000 IU weekly, our loading dose strategy has been chosen to correspond with the standard post-operative clinical follow-up schedule. This is important for generalizability and is likely to overcome potential supplementation adherence issues within the adult fracture population that is often predominantly lower socioeconomic patients. This high loading dose is also in the mid-range of other previous large loading doses used safely in fracture patients and is similar to the total cumulative 3-month dose of our high daily dose group.
- High daily dose: 4,000 IU D₃ represents an alternative high dose strategy and it corresponds to the tolerable upper daily intake level suggested by the Institute of Medicine (IOM).²⁷ While this is the IOM's upper limit, the Endocrine Society has recommended adults can safely take up to 10,000 IU per day,²⁸ further suggesting that our 4,000 IU dose should be well-tolerated.
- Low daily dose: 600 IU D₃ is a common dose and approved indication for maintaining general bone health. 600 IU is also the IOM's Recommended Dietary Allowance for all individuals ages 1-70 years.²⁷ This represents our most conservative supplementation strategy, but its use is common among surgeons prescribing vitamin D and previous studies have shown its efficacy for increasing serum 25(OH)D levels.
- Placebo: Finally, we are including a placebo group because it is important to include placebo-controlled comparisons to our active supplements during this exploratory phase of research. Not only does placebo reflect our usual clinical practice of no supplementation, this Phase II comparison will define our rationale and selection of the control group for the definitive trial. If there are no preliminary efficacy differences between low dose supplementation and placebo, then the low dose supplement could be used as the control group in the Phase III trial. This would obviate potential criticisms for performing a Phase III placebo-controlled trial in a population with a high prevalence of hypovitaminosis D. Given the small number of patients receiving placebo (n=24), the Phase II screening design of this trial, and the fact that receiving placebo does not represent an increased risk of study participation since it is our standard clinical practice, we do not believe this poses an ethical concern. We have used a similar rationale to explain the placebo blinding in the FAITH-2 pilot trial and this has been accepted at over 20 research ethics boards, with no clinical site disallowing the protocol.

3.5.3 Storage and administration

As per the standard operating procedures at the STC, the study supplements/placebo will be stored at room temperature in accordance with the manufacturer's recommendations. The research personnel will maintain an inventory and temperature log to ensure the integrity of the supplements. Study supplementation will begin within 1 week of injury, and it is expected that the research personnel will provide the supplementation to the participant upon discharge from the hospital. Therefore, the hospital pharmacy will not be used to administer this out-patient, over-the-counter medication. The research personnel

have previous experience administering vitamin D supplements/placebo to study patients at the recruiting hospital, the STC.

3.5.4 Potential adverse events associated with vitamin D

A recent systematic review comprehensively examined the effectiveness and safety of vitamin D supplementation among all ages of adult fracture patients.²⁷ The majority of research has been performed in elderly fracture populations; however, the safety of a wide range of doses is well established. Studies with doses of 4,000 IU daily and loading doses from 50,000 IU for up to 7 days or single loading doses up to 500,000 IU have been used without complication.²⁹

Since vitamin D regulates PTH and serum calcium levels, it is theoretically possible that vitamin D supplementation could lead to hypercalcemia. Of the 1,088 patients included in the systematic review, 4 cases of hypercalcemia were reported (0.4%).³⁰ Furthermore, there have been no cases of hypercalcemia in several high loading dose clinical trials. Regardless, we will monitor serum calcium levels at enrolment, 6 weeks, and 3 months post-fracture, and clinical signs of hypercalcemia will be sought at all clinical encounters. If hypercalcemia is identified, participants will be instructed to stop their vitamin D supplementation immediately and the hypercalcemia will be treated as indicated.

Finally, we will monitor for increased falls among the study participants. While we do not expect to observe this adverse event (AE) in our 18 to 50 year-old adult population, a recent study of 200 elderly fracture patients found that a 60,000 IU monthly loading dose and 24,000 IU monthly loading dose plus 300 µg of calcifediol were associated with increased falls compared to the control group.³¹ This single study contradicts several other high loading dose clinical trials, and these concerns have not been borne out of the healthy adult fracture population. This may be a result of the fact that supplementation in the non-osteoporotic fracture population has not been extensively studied (highlighting the need for the proposed research), or because these concerns regarding the risk of falls do not apply to healthy adults without osteoporosis.

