4.2.3 Other Secondary Outcomes

All other secondary outcomes will be presented using point estimates and appropriate measures of variance to describe supplementation adherence, participant safety, and key aspects of participant compliance with the protocol (**Table 4**). Supplement adherence will be summarized using means and 95% confidence intervals for participant self-reporting and the mean cumulative dose taken at 3 months. The incidence of AEs and re-operations for fracture healing complications in each group will be described with counts and proportions. Serum levels of calcium and PTH will be summarized using means and 95% CIs. Participant compliance with the protocol will be summarized descriptively with counts and proportions.

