To determine the effect of low amounts of vitamin D₃ supplementation on fracture healing at 3 months	Low daily dose will increase healing compared to placebo. While the low daily dose is not expected to increase circulating vitamin D as rapidly as the high dose strategies, this comparison will determine if rapid serum increases are necessary to improve fracture healing.	1. FIXIT (Clinical)	Comparisons between the low daily dose & placebo groups will be made using an Independent t-test (alpha=0.20)*
		2. RUST (Radiographic)	
		3. PINP (Biologic)	
		4. CTX (Biologic)	

*Using Phase II screening trial approach, comparisons are non-definitive and an increased alpha level has been adopted.

Table 3: Secondary Outcome Analysis

Objective	Hypothesis	Fracture Healing Outcome	Method of Analysis
To determine if 25(OH)D serum levels are associated with fracture healing at 3 months	There will be an association between fracture healing and: 1) patients' enrolment serum 25(OH)D, 2) their change in 25(OH)D from enrolment to 3 months, 3) their 25(OH)D level at 3 months	1. FIXIT (Clinical)	Associations will be quantified using Univariate Analysis (alpha=0.20)*.
		2. RUST (Radiographic)	
		3. PINP (Biologic)	
		4. CTX (Biologic)	

*Using Phase II screening trial approach, comparisons are non-definitive and an increased alpha level has been adopted.

[figure not shown]
[figure not shown]
[figure not shown]
Table 4: Other Secondary Outcomes Analysis

Objective	Hypothesis	Outcome	Method of Analysis
Supplementation adherence	Daily vitamin D ₃ adherence will be <80% and loading dose vitamin D ₃ adherence will be >95%	Self-report	Summary statistics of means and confidence interval.
		Count of pills	
Participant safety	Adverse events will be rare across all 4 treatment groups.	Adverse event	Summary statistics of proportions.
	Re-operations for a composite of fracture healing complications will follow the same 3 hypotheses as fracture healing.	Re-operations for a composite of fracture healing complications	Summary statistics of proportions.
	Levels of serum calcium will be similar across the 4 treatment groups. Levels of serum calcium will be within normal reference ranges.	Serum Calcium	Summary statistics of means and confidence interval.
	Levels of serum PTH will be similar across the 4 treatment groups. Levels of serum PTH will be within normal reference ranges.	Serum PTH	Summary statistics of means and confidence interval.

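### Falls are to be monitored, but only general adverse event reporting would pick them up: no definition, no solicited question and no separate count by arm

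*Combined protocol and SAP*

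**What the plan says.** Section 3.5.4 discusses two possible harms of supplementation, hypercalcemia and falls. On falls it commits that "we will monitor for increased falls among the study participants". The reason given is one study of 200 elderly fracture patients in which "a 60,000 IU monthly loading dose and 24,000 IU monthly loading dose plus 300 µg of calcifediol were associated with increased falls" compared with control. The section then qualifies the concern. It introduces the study with the words "While we do not expect to observe this adverse event (AE) in our 18 to 50 year-old adult population", says the result conflicts with several other trials of high loading doses, and allows that the risk may not apply to healthy adults without osteoporosis.

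The later safety provisions are general:

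- Sections 3.7.3 and 6.5.1 define an AE broadly enough to include a fall.
- Table 1 schedules AE assessment at 6 weeks and at 3, 6, 9 and 12 months.
- Section 3.7.3 picks out only fracture healing complications from the AEs.
- Section 4.2.3 states: "The incidence of AEs and re-operations for fracture healing complications in each group will be described with counts and proportions".
- Table 4 has one AE row, with the hypothesis "Adverse events will be rare across all 4 treatment groups".

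**The concern.** A commitment to look for an increase implies a comparison between arms, and a comparison needs falls to be counted consistently and shown separately. The plan provides for neither. A participant who stumbled without injury some weeks before a visit has little reason to volunteer it when asked about adverse events in general. If the fall is volunteered, the only AE summary the plan specifies is an overall one.

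What is at stake is the safety information this trial passes on to the phase III dosing trial. The introduction gives dosing safety in immobilized fracture patients as one reason the research is needed. If falls are not asked about, a low count could mean that few occurred or that few were mentioned, and the data could not tell these apart. Falls not asked about at the time cannot be recovered reliably at the end of the study.

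**Working it through.** **1. How the two named harms are carried through the plan**

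| Element | Hypercalcemia | Falls |
|---|---|---|
| Commitment in 3.5.4 | Yes | Yes |
| Time points given in 3.5.4 | Enrolment, 6 weeks, 3 months | None |
| Active search described in 3.5.4 | Serum tests, and clinical signs at every encounter | None |
| Own row in Table 1 | Serum calcium | None; general AE row only |
| Own summary in 4.2.3 | Means and 95% CIs | None; general AE incidence only |
| Own row in Table 4 | Yes, with a hypothesis across the four groups | None; general AE row only |

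The plan turns one named harm into a scheduled, reported measurement and leaves the other to general reporting.

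**2. What general reporting can show**

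The proportion of an arm with any AE counts each participant once. A participant who falls and also has another AE is already in the numerator, so the fall does not change it. When the proportion does differ between arms, it does not say which type of event is responsible. Either way, an increase in falls cannot be read from it.

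**3. Dose comparison, for context only**

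Inputs:
- Reference: 60,000 IU per month (3.5.4).
- Loading arm: "The loading dose of 150,000 IU will consist of 3 50,000 IU capsules" (3.5.1), "given within 1 week of injury and at 6 weeks (+/- 2 weeks) post-injury" (3.4), so two administrations.
- High daily arm: 4,000 IU per day for 3 months (3.4, 3.5.1).
- Low daily arm: 600 IU per day (3.4).

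Monthly equivalents:
- Loading, averaged over 3 months: 2 × 150,000 / 3 = 100,000 IU; 100,000 / 60,000 = 1.7.
- Loading, by the 6-week interval: 150,000 / 42 × 30.44 ≈ 108,700 IU; ratio 1.8.
- Loading, with an 8-week interval: 150,000 / 56 × 30.44 ≈ 81,500 IU, still above 60,000.
- High daily: 4,000 × 30 = 120,000 IU; ratio 2.0.
- Low daily: 600 × 30 = 18,000 IU, below the reference.

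Both high-dose arms exceed the reference in cumulative terms during the 3-month dosing period.

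**4. Why any falls comparison stays descriptive**

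The plan's sample size reproduces. With a difference of 2, SD 3, two-sided alpha 0.20 and power 0.80, n = 2 × (1.2816 + 0.8416)² × (3/2)² = 20.3, rounded up to 21. Then 21 / 0.90 = 23.3, rounded up to 24, and 4 × 24 = 96. It was set for the healing scores and is not affected by this point.

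The documents give no fall rate. Assume that 5%, 10% or 20% of participants fall and that the high-dose arms double this. Power for two proportions at two-sided alpha 0.20 (normal approximation) is then:

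| Assumed rates | 48 vs 48 | 24 vs 24 |
|---|---|---|
| 5% vs 10% | 36% | 27% |
| 10% vs 20% | 54% | 38% |
| 20% vs 40% | 81% | 59% |

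Only the most extreme assumption, with arms pooled in pairs, reaches 80%. Counts and proportions are the suitable summary.

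**The case against.** The strongest reply is that general AE reporting already meets the commitment. Section 3.5.4 itself calls a fall an adverse event, the AE definition covers it, five visits assess AEs, and AE incidence is described by group. This stands to the extent that a reader might infer that no visit, outcome or table captures falls, and the documents do not support that. A reported fall has a place to be recorded and would be counted. What the reply does not supply is a way to elicit falls that are not volunteered, or a display that separates them.

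Second, the protocol does not expect falls in this age group and rests the concern on one contradicted study in elderly patients. That is fair and keeps the point minor. But the protocol made the commitment with those qualifications in view, and it says the absence of such findings in healthy adults may reflect how little this population has been studied.

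Third, the dose ratios could be read as evidence of raised risk in the high-dose arms. They are not. The cited study gave monthly doses to elderly patients, one arm here is dosed daily, and the other regimen linked to falls contained only 24,000 IU monthly plus calcifediol, so no dose-response is established. Nor are falls the only harm singled out; hypercalcemia is discussed first and at greater length.

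Fourth, Section 4.2.3 does not say that AEs will be pooled into a single figure, and the case report forms (CRFs) are not among the documents. A breakdown by type or a falls prompt may be intended. If so, the plan need only say so.

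**Conclusion.** The point holds as a minor inconsistency within the plan. Section 3.5.4 commits to monitoring for increased falls, and the provisions that follow rely on general AE reporting, with no definition, solicited question or separate count by arm. Under-reporting of falls without injury is likely, and an overall AE proportion cannot show an increase.

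The size of the under-reporting cannot be calculated, because the documents give no fall rate. The conclusion assumes that the CRFs contain no falls prompt and that no AE breakdown by type is planned beyond what is written. It does not depend on the dose comparison, and it implies no view on any dose. The primary and secondary aims, the sample size and the planned tests are untouched. Even with the fix, 24 participants per arm would support description rather than a conclusion about whether falls differ.

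**What to change.** - Define a fall in Section 3.7.3.
- Add a solicited item to the existing AE assessment: any fall since the last visit, how many, and whether any caused injury. Ask it at least at the 6-week and 3-month visits, which cover the dosing period; the later visits are optional.
- Add a sentence to Section 4.2.3 and a descriptive row to Table 4 giving, by arm, the number and proportion of participants with at least one fall and the total number of falls. Specify no formal test.

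If the CRF already asks about falls, only the definition and the reporting changes are needed. The cost is about a minute per visit at visits already held, and one table row.

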3.5.5 Concomitant calcium supplementation

In addition, although calcium supplementation is often recommended concomitantly with vitamin D for osteoporosis prevention, for our non-osteoporotic study population the necessity of calcium supplementation is controversial and will not be provided because of the increased risk of kidney stones, hypercalcemia, and potential confounding. This rationale has also been outlined by other researchers performing RCTs involving vitamin D supplementation.

3.6 Surgical Technique and Post-Operative Rehabilitation

3.6.1 Surgical technique

The study protocol will not dictate the surgical technique. Based on the study's eligibility criteria, all participants must receive a reamed, locked, intramedullary nail for their tibial or femoral shaft fracture. The number and orientation of locking screws is at the discretion of the treating surgeon, as there have been no studies that demonstrate clinical superiority

of any locking screw strategy. Any concomitant fracture lines that extend into the adjacent articular areas may be treated with additional fixation as indicated.

3.6.2 Post-operative rehabilitation

Full weight-bearing as tolerated is recommended for all isolated tibial and femoral shaft fractures. In the presence of additional lower extremity fractures, intra-articular extension, or other concomitant soft tissue injuries, participants may be restricted to protected weight-bearing (partial or no weight) for up to 6 weeks post-fracture. If additional contralateral injuries are present, both limbs must be eligible for full weight-bearing by 6 weeks post-fracture.

3.7 Primary and Secondary Outcome Measures

3.7.1 Primary outcome

Fracture healing will be assessed as follows: 1) clinical fracture healing will be measured using FIX-IT, 2) radiographic fracture healing will be measured using the RUST, and 3) biological fracture healing will be measured using serum levels of CTX and PINP.

Clinical Healing: FIX-IT is a standardized measure of weight-bearing and pain in patients with lower extremity fractures, specifically tibia and femur fractures.¹⁸ Preliminary validation of the FIX-IT has demonstrated high inter-rater agreement and moderate correlation with the physical scores of the Short Form-36.¹⁸ It has been used in other studies to assess clinical fracture healing.

Radiographic Healing: The RUST score assesses the presence of bridging callus or a persistent fracture line on each of 4 cortices.¹⁹⁻²² This score has been previously validated and found to have greater inter-rater reliability when compared with surgeons' general impression of the cortical bridging.¹⁹⁻²² RUST has been widely used to assess radiographic fracture healing.¹⁹⁻²² An orthopaedic surgeon who is independent of the study will review the images and assign a RUST score.

Biological Healing: CTX is a bone-resorption marker and previous research has found that it rises 1 week after fracture of the tibial shaft and remains elevated throughout fracture healing.²³ PINP is a bone-formation marker and prior research has found that it is highest at 12 weeks after fractures of the tibial shaft and proximal femur.³²

The primary time point for assessing fracture healing will be at 3 months post-injury. This time point was selected because it coincides within the standard clinical follow-up schedule, and because it has the greatest potential to detect differences in short-term fracture healing. While we expect the 1-year fracture union rate to be approximately 95% for the femur fractures³² and 75% for the tibia fractures (unpublished data from the SPRINT trial),⁷ improved early fracture healing is biologically plausible. The median time to fracture union for tibia fractures is 4 months; therefore, many patients are still experiencing morbidity from their injury at the 3-month visit and decreasing the time to union would be an important patient benefit.

